### **6.4.7 Laboratory Analyses**

Any abnormal laboratory test (hematology, clinical chemistry, or urinalysis) or other safety assessment results (eg, ECGs, radiological scans, vital sign measurements), including those that worsen from baseline, believed to be clinically significant in the medical and scientific judgment of the investigator are to be recorded as AEs or SAEs.

However, any clinically significant laboratory assessments that are associated with the underlying disease, unless judged by the investigator to be more severe than expected for the subject's condition, are not to be reported as AEs or SAEs.

### 6.4.8 Hematology

Tests will include the following:

Hemoglobin	Differential:
Hematocrit	Neutrophils
Red blood cells	Lymphocytes
White blood cells	Monocytes
Red cell indices	Basophils
Platelet count	Eosinophils
	Prothrombin time
	Partial thromboplastin time
	Haptoglobin

### 6.4.9 Blood Chemistry

Tests will include the following:

Alanine aminotransferase	Chloride	Phosphorus
Albumin	Creatinine	Potassium
Alkaline phosphatase	Fasting insulin level	Sodium
Aspartate aminotransferase	$\gamma$ -glutamyl transferase	Total and direct bilirubin
Bicarbonate	Glucose	Total protein
Blood urea nitrogen	Lactate dehydrogenase	Uric acid
Calcium	Magnesium	

### 6.4.10 Urinalysis

Refer to the Study Manual for collecting urinalysis samples. Tests will include the following:

Color	Glucose	Red blood cells
Clarity	Blood	Hyaline and other casts
pH	Bilirubin	Bacteria
Specific gravity	Leukocyte esterase	Epithelial cells
Ketones	Nitrite	Crystals
Protein	White blood cells	Yeast

### 6.4.11 Alcohol TLFB

Current alcohol consumption will be assessed during the treatment phase ([Table 12-2](#)) using the Alcohol TLFB. The Alcohol TLFB is a drinking assessment method that obtains estimates of daily drinking and has been evaluated with clinical and nonclinical populations. Using a

calendar, subjects will provide retrospective estimates of their daily drinking over a specified time period. The Alcohol TLFB will be given to the subject at the beginning of the visit (Table 12-2), and will be considered source documentation.

Subjects should be instructed to refrain from regular alcohol use during the study. If subjects are found on the calendar to be drinking greater than or equal to 7 standard alcoholic drinks per week, they will be asked to stop drinking or reduce their intake. The Alcohol TLBF Calendars for the years 2015, 2016, and 2017 along with instructions are provided in Section 12.4.

## 6.5 Pharmacokinetic Assessments

Plasma levels of GR-MD-02 will be assessed in all subjects (Table 12-2). Plasma levels of GR-MD-02 will be assessed 2 hours following the infusion of IMP in all subjects after Infusion Visits 1, 2, 3, 4, 7, 10, 13, and 26. At the first data safety monitoring board (DSMB) meeting, the panel will evaluate GR-MD-02  $C_{max}$  plasma levels after Infusion Visits 1, 2, 3, and 4 for the first 30 subjects.

Blood samples for bioanalytical assay will be handled as described in the Study Manual. The date of PK blood collection must be recorded in the subject's eCRF. Each label will state the study number, subject number, matrix (plasma), and study day of the sample.

## 6.6 Sample Collections

All safety laboratory tests will be collected after the subject has been fasting for at least 8 hours. Each subject will have blood drawn for hematology and chemistry (including fasting insulin level). Refer to the Study Manual for instructions for sample handling and shipping.

## 7 Statistical and Analytical Plan

A summary of statistical methods is presented in the following sections and will be described in more detail in the statistical analysis plan (SAP).

### 7.1 Primary Efficacy Endpoint

The primary efficacy endpoint analysis is the baseline-adjusted change in HVPG at 1 year (53-55 weeks) in subjects treated with placebo as compared to subjects treated with GR-MD-02 (2 mg/kg/week or 8 mg/kg/week).

### 7.2 Secondary Efficacy Endpoints

The secondary endpoints are:

- The baseline-adjusted absolute change in the CPA at 1 year as determined by digital morphometric analysis of liver biopsies
- The baseline-adjusted change in liver stiffness as determined by FibroScan score prior to the first infusion, at Infusion Visit 13, and 14-28 days after final infusion
- The baseline-adjusted change in the metabolic capacity of the liver as determined by cPDR30 of the MBT (if available) at screening, Infusion Visit 13, and 14-28 days after final infusion
- The difference between GR-MD-02-treated and placebo-treated subjects in the progression of cirrhosis at 1 year, defined as the development of any of the following:
  - esophageal variceal hemorrhage or portal hypertensive gastropathy hemorrhage (confirmed by endoscopy or interventional radiology)
  - clinically apparent ascites
  - spontaneous bacterial peritonitis
  - overt hepatic encephalopathy

- an increase in Child-Turcotte-Pugh score  $\geq 2$
- newly diagnosed varices in a subject without prior varices
- progression from small to medium or large varices
- qualification for liver transplant defined as a MELD score  $\geq 15$
- listing for a liver transplant or the performance of a liver transplant
- liver-related mortality

### **7.3 Exploratory Endpoints**

Exploratory endpoints are to evaluate:

- Difference in health-related quality of life (using the subject-completed CLDQ) following administration of GR-MD-02 or placebo at 1 year
- Baseline-adjusted change in FibroTest (FibroSure) and ELF score at Infusion Visits 7, 13, 20, and 14-28 days after final infusion
- Changes in liver biopsy staining for alpha smooth muscle and galectin-3 in subjects treated with GR-MD-02 or placebo at 1 year
  - HVPG  $\geq 10$  and  $< 15$  mm Hg (elevated portal pressure, with potential development of varices, classified as clinically significant portal hypertension)
  - HVPG  $\geq 15$  (increased incidence of complications from varices)

### **7.4 Safety Endpoints**

The safety endpoints include the incidence of AEs during study treatment, emergent physical examination abnormalities, emergent vital sign and ECG abnormalities, and laboratory parameter abnormalities.

## 7.5 Pharmacokinetic Endpoint

The PK endpoints include plasma concentrations and population PK parameters of GR-MD-02.

## 7.6 Sample Size Calculations

A total of approximately 156 subjects will be enrolled in the study. Sample size calculations are based on the comparison of the primary efficacy variable, change in HVPG from baseline, with the following assumptions (key assumptions discussed as follows):

1. True mean change in HVPG from baseline at 52 weeks in the placebo group,  $\Delta p = 0$
2. True mean change in HVPG from baseline at 52 weeks in either GR-MD-02 dose group,  $\Delta G = -2$  mm Hg
3. Common SD for difference in HVPG,  $\sigma = 3$  mm Hg
4. Null hypothesis,  $H_0: \theta = G - \Delta p = 0$
5. Type I error,  $\alpha = 0.05$  (2-sided significance test)
6. Power = 80%
7. Statistical test = 2-sample  $t$ -test for mean difference
8. Randomization ratio = 1:1:1
9. Drop-out rate of 25%

For a mean difference of 2 mm Hg and accounting for a 25% dropout rate, the total sample size of 156 subjects ( $n = 52$  subjects per group) will be required to achieve power of 80% with a 2-sided type I error rate of 0.05.

## Discussion of assumptions:

1. True mean change in HVPG from baseline at 52 weeks in the placebo group was set at 0 mm Hg. While one might assume that the fibrosis would progress over a 1-year period and there might be a resultant increase in HVPG, the conservative assumption was made that there would be no change.
2. True mean change in HVPG from baseline at 52 weeks in either GR-MD-02 dose group was set at 2 mm Hg. A reduction of 2 mm Hg in HVPG was chosen because a change of this degree is likely to be of clinical significance. The results of pharmacological therapies, such as nonselective  $\beta$ -blockers have been remarkably consistent across therapeutic studies. If the HVPG is reduced by at least 20% from baseline, the risk of variceal bleeding, rebleeding, and other complications of portal hypertension such as ascites, spontaneous bacterial peritonitis and hepatorenal syndrome markedly decreases and survival improves (VillanuevaVillanueva 2009; Escorsell 2000; Abraldes 2003). In addition, a 10% reduction in HVPG has been shown to prevent the development of varices (Groszmann 2005). Therefore, it appears that a reduction in HVPG between 10% to 20% confers clinical benefit of reduced variceal bleeding. It is anticipated that the mean HVPG for the experimental groups will be between 10 mm Hg and 15 mm Hg, as in other similarly designed studies (Groszmann 2005). Therefore, a 2 mm Hg change in HVPG between placebo and treated groups would be between 15% and 20%, which is likely to be of clinical significance.
3. The common SD for difference in HVPG over 1 year for subjects in the placebo group was set at  $\sigma = 3$  mm Hg. This assumption was determined from primary data, obtained from the investigator ([name]), from a longitudinal clinical study (Groszmann 2005). Table 7-1 and Table 7-2 show data for subjects in the placebo group who had baseline and 12-month HVPG measurements ( $n = 82$ ), of which 32 subjects had a baseline HVPG  $<10$  mm Hg and 50 subjects had a baseline HVPG  $\geq 10$  mm Hg. From these data, the SD of the absolute change at 12 months in the placebo group was 2.85 mm Hg. Therefore, the assumption of 3 mm Hg for the sample size calculation appears valid.

**Table 7-1 HVPG (mm Hg) at Baseline and 12 Months for Subjects in the Placebo Group in the Timolol Clinical Study**

Treatment	Variable	N	Mean	SD	Median	Lower Quartile	Upper Quartile	Min	Max
Placebo	HVPG Baseline	82	11.29	3.97	10.75	8	14	6	23.5
Placebo	HVPG 12 mo	82	10.98	3.82	10.9	8	14	4	22.0

Abbreviations: Max, maximum; min, minimum; SD, standard deviation

Source: [Groszmann 2005](#)

**Table 7-2 Absolute Change in HVPG (mm Hg) at 12 Months for Subjects in the Placebo Group in the Timolol Clinical Study**

Treatment	N	Mean	SD	Median	Lower Quartile	Upper Quartile
Placebo	82	0.31	2.85	0.5	-1	2

Abbreviation: SD, standard deviation

Source: [Groszmann 2005](#)

## 7.7 Analysis Sets

The following analysis sets will be used in the statistical analyses.

**Full-Analysis set (FAS):** The FAS, or intent-to-treat group, will consist of all subjects who were randomly assigned to IMP. All analyses using the FAS will group subjects according to randomized treatment. The FAS will be used as the primary efficacy analysis set.

**Modified-Intent-to-Treat analysis set:** The modified intent-to-treat set will consist of all subjects who were randomly assigned, received at least 1 infusion, and had at least 1 postbaseline efficacy assessment (from [Section 6.2](#)). All analyses using the modified intent-to-treat set will group subjects according to randomized treatment.

**Per-protocol set:** The per-protocol set will consist of all FAS subjects who have at least 80% compliance with study treatment, have not taken any prohibited medication, have no significant protocol deviations, and restricted to each subject's time on IMP plus 30 days thereafter for the analysis of progression of efficacy events. All analyses using the per-protocol set will group subjects according to treatment actually received.

Safety set: The safety set will consist of all subjects who received any IMP. All analyses using the safety set will group subjects according to treatment actually received.

Pharmacokinetic set: The PK analysis set will consist of subjects who provide at least 1  $C_{max}$  PK sample.

## 7.8 Description of Subgroups to Be Analyzed

No subgroup analyses are planned.

## 7.9 Statistical Analysis Methodology

Statistical analysis will be performed using SAS software Version 9.1.3 or later. Continuous variables will be summarized by randomized treatment group using the mean, the SD, median, 25th and 75th percentiles, minimum value, and maximum value. Point estimates and the associated 95% confidence interval for the difference in baseline-adjusted efficacy parameters will be summarized in a similar manner. Categorical variables will be summarized by randomization treatment group using frequency counts and percentages. All baseline and postbaseline data used for safety and efficacy evaluations will be listed in data listings.

Baseline is defined as the last assessment prior to infusion with IMP (ie, the predosing assessment present in the database that is most proximate to the time of IMP administration). Measurements that are obtained after the first dose of study treatment will be considered postbaseline values. Change from baseline is defined as the postbaseline value minus the baseline value.

All statistical tests will be 2-sided and will be at the 5% level of significance. Due to the small number of subjects expected to be enrolled at each study center, all summaries and analyses will be performed using data pooled across study centers. Any imbalances in subject enrollment at study centers will be reviewed and methods for accommodating/eliminating the potential effect on efficacy analyses will be addressed in the SAP.

For analysis variables that are not normally distributed, alternative methods will be applied including the use of the Poisson-regression model (or the negative binomial) for counts data.

For others, a nonparametric method based on Hodge-Lehmann estimate (or similar) and associated 95% confidence interval on median difference will be applied ([Hodges 1963](#)).

Methods for dealing with missing data including dates, efficacy and safety results will be specified in the SAP.

Details of the statistical analyses, methods, adjustments for multiplicity, and data conventions will be described in the SAP.

### **7.9.1 Analysis of Primary Efficacy Endpoint**

The primary efficacy endpoint analysis is the baseline-adjusted change in HVPG at 1 year (53 to 55 weeks) in subjects treated with placebo as compared to subjects treated with GR-MD-02 (2 mg/kg/week or 8 mg/kg/week). Change in HVPG from baseline will be compared between treatments groups using analysis of covariance adjusted for baseline HVPG. Treatment group will be included in the model as indicator variables where  $T1 = 1$  if subject is randomly assigned to 2 mg/kg/week and 0 otherwise and  $T2 = 1$  if subject is randomly assigned to 8 mg/kg/week and 0 otherwise. The following hypotheses will be tested based on the parameter estimates (and standard errors) from the fit of the analysis of covariance model:

$H01: \Delta T1 - \Delta p = 0$  vs  $HA1: \Delta T1 - \Delta p \neq 0$

$H02: \Delta T2 - \Delta p = 0$  vs  $HA2: \Delta T2 - \Delta p \neq 0$

The closed testing procedure of Bonferroni-Holm (1988) will be used to adjust for multiple comparisons of each GR-MD-02 dose (T1 and T2) with placebo so that overall type I error rate is preserved at 0.050 (2-sided). If at least 1 of 2 doses is found to be significantly better than placebo, the 2 doses will be compared with each other at the 0.05 level to address dose response.

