4.1. Sample Size

The sample size of 52 subjects per treatment arm assumes a mean difference in the change of HVPG from baseline at 52 weeks between an active treatment arm and placebo of 2 mm Hg with a SD of 3 mm Hg, and allows for a 25% dropout rate and 80% power to detect a statistically significant difference at an α level of 0.05. A difference of 2 mm Hg in the change of HVPG is considered to be of “clinical significance” (Villanueva 2009; Escorsell 2000; Abraldes 2003). The SD of 3 mm Hg at a mean change of HVPG of 2 mm Hg from baseline is based on primary data, obtained from an investigator ([name]), as reported in a published longitudinal clinical study (Groszmann 2005).

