4.2. Randomization, Stratification, and Blinding

Approximately 156 eligible subjects will be randomly assigned to one of the following 3 treatment groups in a 1:1:1 ratio:

- Approximately 52 subjects are assigned to GR-MD-02 in dose of 2 mg/kg LBM
- Approximately 52 subjects are assigned to GR-MD-02 in dose of 8 mg/kg LBM
- Approximately 52 subjects are assigned to placebo

The randomization mechanism for the study will be deployed within an interactive web response system (IWRS). Unblinded biostatisticians will generate the randomization schedule using SAS software Version 9.2 or later for IWRS which will link sequential subject randomization numbers to treatment codes allocated at random with a 1:1:1 randomization ratio.

Except in an emergency, investigators, Galectin, or other persons involved in study conduct will not know the randomization schedule and study drug allocation before study completion. The IWRS system will be used if emergency unblinding is required. This would generally only be used in an emergency, when knowledge of the actual treatment becomes medically necessary.

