8.1.1. Primary Analysis

The primary efficacy endpoint, change from baseline in HVPG at 1 year (53 to 55 weeks), will be analyzed using analysis of covariance (ANCOVA) with baseline values taken as a covariate using the FAS population at a significant level of 0.05 (2-sided). Treatment effect will be evaluated as a contrast of each active treatment versus placebo and described using continuous summary. To control the type I error rate due to multiple comparisons, the Bonferoni-Holm (1988) procedure for the comparison between treatment group and control will be implemented. Estimate of mean difference along with 95% CI will also be presented.

Missing HVPG at 1 year will be imputed using the last observation carried forward (LOCF) method. The sensitivity analysis will be performed on the change from baseline in HVPG based on the LOCF values in the FAS population using the same statistical methodology described above.

Additional sensitivity analyses for HVPG will include:

- Change from baseline in HVPG at 1 year in the MITT population.
- Change from baseline in HVPG at 1 year in the PP population.

The following subgroup analysis will also be conducted in the MITT population:

- Change from baseline in HVPG at 1 year by baseline HVPG category of MPH and CSPH
- Change from baseline in HVPG at 1 year by gender.
- Percentage of subjects who have $\geq 10\%$ and $\geq 20\%$ decrease at 1 Year in HVPG by baseline HVPG category of MPH and CSPH
- Percentage of subjects with HVPG at CSPH level at Baseline and at MPH level at 1 Year

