

Huber, PJ. Robust Regression: Asymptotics, Conjectures and Monte Carlo. *Annals of Statistics*. 1973;1, 799–821.

Galectin Therapeutics Inc

GT-026

**A Multicenter, Randomized, Placebo-Controlled, Double-Blind,
Parallel-Group, Phase 2 Clinical Trial to Evaluate the Safety and Efficacy
of GR-MD-02 for the Treatment of Liver Fibrosis and Resultant Portal
Hypertension in Patients with NASH Cirrhosis**

The NASH-CX Trial

26 Jan 2018

Statistical Analysis Plan Addendum

Version 2.0

Prepared by:

PPD

[name]
[name]

The additional data analysis as listed below will be performed as post-hoc analysis. The main objective is to repeat primary and secondary analysis on the following subgroups:

- a. Patients with baseline (BL) varices, and patients without BL varices.
- b. Patients with MPH (baseline HVPG 6 to <10 mmHg) and patients with CSPH (baseline HVPG \geq 10 mmHg)

For definition of analysis set and other terminology or abbreviation, please refer to final SAP. However, the subject who was randomized but have not received any treatment will be removed from all analysis sets used in post-hoc. In addition, the missing value at scheduled visit will be imputed by result from subsequent unscheduled visit. For example, if a subject's HVPG at Week 53-55 visit was not collected, but there's a subsequent unscheduled visit with valid result, this unscheduled result will be used as subject's HVPG result at Week 53-55.

For LOCF analysis, include all patients that had an early termination visit, and carry forward their last observation result.

Analyses on Primary Endpoint HVPG

1. Perform ANCOVA to determine effect of varices on HVPG on FAS LOCF dataset:
 - a. Week 53/55 HVPG is used as dependent with BL HVPG as covariate, and with dose, varices and dose varices interaction as fixed factors.
2. Run ANCOVA for FAS LOCF, mITT LOCF, and PP LOCF for HVPG with Least square difference (LSD) mean comparison (no Bonferroni correction) on subset of patients with / without baseline varices:
 - a. BL Change in HVPG vs dose with BL HVPG as a covariate (i.e. adjust for baseline HVPG)

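### The primary HVPG analysis could prespecify baseline varices as a covariate and use step-down Dunnett instead of Holm; the cost is minimal, but the gain is small for Dunnett and conditional for varices

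*Protocol*

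**What the plan says.** **Model.** Protocol 7.9.1 fits one ANCOVA with two dose indicators and baseline HVPG: "Change in HVPG from baseline will be compared between treatments groups using analysis of covariance adjusted for baseline HVPG". SAP 8.1.1 has the same model, "with baseline values taken as a covariate using the FAS population".

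**Multiplicity.** Protocol 7.9.1: "The closed testing procedure of Bonferroni-Holm (1988) will be used to adjust for multiple comparisons". SAP 8.1.1 keeps this procedure. Each dose is compared with the same placebo arm.

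**Randomization.** SAP 4.2 has stratification in its title but names no factor. It describes a list of "treatment codes allocated at random with a 1:1:1 randomization ratio". Protocol 5.1 names no factor either.

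**Varices.** Protocol 6.1.2 and 6.2.7 require an EGD within 2 months before randomization, and protocol 4.1.2 excludes medium and large varices. Each randomized subject is therefore known to have no varices or small ones. Neither the protocol nor the main SAP uses varices as a covariate, stratum or subgroup. They first enter an HVPG model in the SAP Addendum of 26 January 2018, which is labelled post hoc. That model is fitted "with dose, varices and dose varices interaction as fixed factors", and separate analyses follow for subjects with and without varices.

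**The concern.** Under unstratified randomization, a baseline variable left out of the model can differ between arms by chance, and whatever outcome variance it explains stays in the error term. Adjusting for one already collected binary variable costs one degree of freedom.

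Holm protects the familywise error under any dependence between the two tests. Here the dependence is known: with equal arms and a shared control the contrasts correlate at 0.5. A procedure that uses this correlation can spend the part of the 5% that Holm leaves unspent.

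At stake is modest precision in the primary comparison. The sizing does not split alpha over the two doses, so small gains that need no extra patients are worth having.

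**Working it through.** **1. The plan's sample size.** Inputs are from protocol 7.6 and SAP 4.1: difference 2 mm Hg, SD 3 mm Hg, two-sided alpha 0.05, 80% power, two-sample t-test, 25% dropout.
- Normal approximation: n = 2(1.960 + 0.842)² × (3/2)² = 35.3, so 36 per arm; 36/0.75 = 48.
- Exact noncentral t: 37 per arm; 37/0.75 = 49.3, so 50.
- The plan has 52, slightly generous. 52 × 0.75 = 39 evaluable per arm gives 82.8% power at alpha 0.05. The same t-test at 0.025 (Holm's first step) gives 74.3%.

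**2. Holm against step-down Dunnett.** Setting: 39 per arm, SD 3, pooled error, contrast correlation 0.5.
- First-step critical value: Holm 2.271 (t quantile at 0.9875, 114 df; 2.272 on the 113 df left after baseline HVPG). Dunnett, by numerical integration: 2.240, a nominal p of 0.0270 instead of 0.0250.
- The second step is the unadjusted 0.05 test in both. Dunnett therefore rejects whenever Holm does.

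Simulated results:

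| Scenario | Holm | Step-down Dunnett |
|---|---|---|
| Familywise error, neither dose works | 4.6% | about 5% |
| One dose works: power for that dose | 75.0% | 75.9% |
| Both work: at least one rejected | 87.7% | 88.4% |
| Both work: both rejected | 72.2% | 72.4% |

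**3. Adding varices.** Let r be the partial correlation of varices with HVPG change given baseline HVPG. The residual SD becomes 3 × √(1 − r²), with 1 df lost. The documents give no value for r, so a range is shown. Power is for the one effective dose.

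| Assumed r | Residual SD | Holm | Step-down Dunnett |
|---|---|---|---|
| 0 | 3.00 | 75.0% | 75.9% |
| 0.1 | 2.985 | 75.4% | 76.4% |
| 0.2 | 2.939 | 76.8% | 77.8% |
| 0.3 | 2.862 | 79.3% | 80.1% |

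At r = 0 the lost degree of freedom costs under 0.1 point.

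**4. The adjustment already planned.** Protocol Tables 7-1 and 7-2 give placebo SDs of 3.97 (baseline), 3.82 (12 months) and 2.85 (change).
- Correlation = (3.97² + 3.82² − 2.85²)/(2 × 3.97 × 3.82) = 22.23/30.33 = 0.73.
- Residual SD after baseline adjustment = 3.82 × √(1 − 0.733²) = 2.60.
- With 2.60 in place of 3, Holm power for one effective dose is 87.0%, and Dunnett alone gives 87.7%. Both changes together give 88.0%, 89.1% and 90.7% at r = 0.1, 0.2 and 0.3.

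**5. Chance imbalance.** Prevalence of varices is not given; take 30% to 50%. The SD of the difference in prevalence between two arms of 39 is √(2p(1 − p)/39) = 0.104 to 0.113. A difference above 15 percentage points then arises in 14.8% to 18.5% of dose-placebo comparisons. If varices shifted HVPG change by an assumed 1 mm Hg, a 15-point difference would move the contrast by 0.15 mm Hg. The contrast's standard error is 3 × √(2/39) = 0.68.

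**The case against.** The strongest reply is that the plan is already valid and that this is a choice between sound methods. Much of it stands.

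- **Prognostic value is not shown.** A reader might infer that leaving out varices certainly wastes power. No document shows that varices predict HVPG change beyond baseline HVPG. Protocol 7.3 itself links varices to the HVPG level, so part of any signal is already captured. The addendum's later use of varices is not evidence of prognostic value.
- **The starting power may be better than it looks.** A reader might take 74% or 75% as the power of the planned test. Those figures use SD 3 and give no credit for the baseline-HVPG adjustment. If the historical data carry over, the figure is about 87%.
- **Imbalance is not bias.** Chance imbalance is already covered by the standard error and the type I error rate, and the illustration in step 5 is small beside both.
- **The addendum asks something else.** A reader might think that a varices term would have settled the addendum's question in advance. That question is effect modification: an interaction and separate subgroup analyses. A main effect does not answer it.
- **Holm is more portable.** Protocol 7.9 allows a nonparametric fallback for non-normal variables. Holm carries over to it unchanged; normal-theory Dunnett critical values do not.
- **The factor is not cleanly defined.** Protocol 4.1.2 describes small varices as more than 25% of the lumen, protocol 6.2.7 as less than 25%. No central EGD reading is described, whereas HVPG tracings are read centrally (6.2.1).

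None of this removes the two points that remain. Step-down Dunnett is never worse than Holm under assumptions the ANCOVA already makes, and a varices main effect costs almost nothing even if it proves uninformative.

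**Conclusion.** The point holds as an optional, low-cost improvement. It is not an error in the plan: type I error is controlled and the primary estimate is valid as written.

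The Dunnett gain is certain but small: 0.2 to 1.0 point at SD 3 with 39 per arm, depending on the scenario. It rests on normal errors, a common variance and the shared placebo arm.

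The varices gain is conditional. At SD 3 it ranges from a loss under 0.1 point at r = 0 to about 0.5 to 4 points for r of 0.1 to 0.3, and that range is assumed. With a residual SD of 2.60 both gains shrink. Neither change should be presented as repairing the sizing: at SD 3, the two together reach 80% for a single effective dose only near r = 0.3.

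**What to change.** In protocol 7.9.1 and SAP 8.1.1, before unblinding:

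1. Add baseline varices (absent/present, from the screening EGD) to the primary ANCOVA as a main effect. Keep the model with baseline HVPG alone as a sensitivity analysis.
2. Replace Bonferroni-Holm by step-down Dunnett for the two dose-placebo contrasts, with the correlation taken from the fitted model, since unequal numbers of completers move it from 0.5. Keep Holm if the nonparametric fallback in protocol 7.9 is used.
3. Reconcile the definitions of small varices in protocol 4.1.2 and 6.2.7. Absent/present coding is less affected by the conflict than size grading, but not immune to it.
4. If effect modification by varices is of interest, prespecify it separately; the main effect does not cover it.

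The cost is a change of wording and one degree of freedom, with no new data, visits or patients. Once the data are unblinded, these analyses can only be supportive.
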